9.4 Sample Size

We anticipate no more than 20% dropout during the 4-week intervention, which would result in about 24 observations at each of the 4 doses. This sample size would allow us to estimate the effect size of the optimal dose within 0.37 units (80% CI), or 0.57 (95% CI), which is considered an adequate level of evidence for the goals of the grant (R61) mechanism. Note that the analytic method is mixed effects model which will provide somewhat better power than the one reported above under worst-case scenario. Also of note, we observed a large effect size for BOLD signal changes ($d=1.54$) during t-PBM in the right MFG in our preliminary data¹⁰³

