3.1 Primary Objective

Our primary objective is to identify the t-PBM irradiance dose (50, 300, or ≥ 700 mW/cm 2) with the largest impact on PFC CBF in MDD.

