3.5 Study Endpoints

3.5.1 Primary Study Endpoints

The primary endpoint will be t-PBM effects on BOLD signal.

The specificity of t-PBM effects on BOLD signal increases will be assessed by testing three irradiance doses covering a wide range (50, 300 and ≥ 700 mW/cm 2) versus sham. If a reliable effect on BOLD (compared to sham, the BOLD increase at the optimal dose will have an effect size of Cohen's $d \geq 0.5$) is seen with PBM, the study validate BOLD fMRI as a robust biomarker of target engagement for t-PBM and act as a "go" signal. In contrast, if none of the t-PBM doses yield reliable BOLD increases, this will fail the putative mechanism (*no go*).

Rationale for the effect size (E.S.) threshold: We have previously observed large effect size changes in BOLD (Cohen's $d=0.6$) after a single administration of t-PBM (at 318 mW/cm 2)¹⁰³. In our clinical pilot study, significant, large effect size improvements in depressive symptoms were reported in MDD after 8 weeks (Cohen's $d=1.5$, $n=21$)³⁵. Given these preliminary results, we will use as threshold for the Go/No-Go decision an effect of t-PBM on BOLD at one dose (but not all doses, vs. sham) of magnitude Cohen's $d > 0.5$ (at least medium size).

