4.3 Strategies for Recruitment and Retention

We intend to enroll 30 subjects over 24 months. We believe that our combined track record of recruitment in previous MDD research (see below) and our existing referral sources described below show the feasibility of recruiting sufficient numbers of MDD patients for this study.

This trial will recruit patients at two independent sites: 1) NYU and Nathan Kline Institute (NKI), acting as a single site with two locations in the greater New York City area, and 2) Massachusetts General Hospital (MGH), in Boston, MA. The two sites (NYU/NKI and MGH) will each be responsible for enrolling 50% of the total sample. We anticipate completing the R61 within 22 months, with fMRI data analyzed on a rolling basis.

At NYU, participants will be enrolled by the Mood Disorders Research Program, led by [name], which has an excellent track record of recruitment in studies involving the assessment and treatment of subjects with MDD. Participants with MDD will primarily be recruited from the NYU Langone Medical Center (NYUMC) Outpatient Psychiatry Department and from the NYU Bellevue Hospital, as well as from an extensive network of community partners, supplemented with local advertising and recruitment outreach efforts. We have strong relationships with the NYU Langone OPD, where currently 500 MDD patients receive on-going treatment and approximately 300 new bipolar disorder patients are evaluated every year. NYU Bellevue Hospital, with 330 inpatient mental health beds, has \geq 200 admissions of MDD patients per year. We will have periodic meetings with the Psychiatry staff at NYU Langone and at Bellevue Hospital to facilitate referrals to our study. We are also able to recruit through our relationship with NYU-affiliated community psychiatric clinics in Manhattan and Brooklyn, and with NYU Langone Brooklyn (formerly Lutheran Hospital in Brooklyn), where we have traditionally received referrals from clinicians and from posting NYU IRB-approved advertisements. To further increase our potential enrollment for this study [name] has established relationships with the Mood Disorders Support Group of New York (MSDG/NY),

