9.3 Description of Statistical Methods

9.3.1 General Approach

Before any statistical techniques are applied, the distribution of all variables will be investigated using descriptive statistics and outliers will be examined. Where necessary, non-parametric statistical methods will be used rather than relying on distributional assumptions. Since the main goal of the study is to obtain evidence about the mechanism of action, the feasibility of implementation, and the potential for efficacy of novel treatment strategies that, if warranted, will be tested in future confirmatory studies, the emphasis of the statistical analysis will be on estimation (with effect sizes and confidence intervals) rather than on hypothesis testing. Where formal hypothesis testing is employed, significance will be judged at 5% level, two-sided.

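### The precision quoted for the optimal dose is that of a dose named in advance; choosing the best of three biases its estimate upward, towards Go

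*Combined protocol and SAP*

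**What the plan says.** Section 3.1 sets the primary objective as finding the irradiance "with the largest impact on PFC CBF in MDD". Section 9.3.2 fits one mixed model to the four conditions and estimates each active dose's difference from sham, which gives three contrasts sharing one sham mean. Section 3.5.1 bases the Go/No-Go decision on the leading dose: "the BOLD increase at the optimal dose will have an effect size" of Cohen's d at least 0.5 against sham. It adds that the effect should appear at one dose but not at all of them.

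Section 4.3 plans 30 participants. Section 9.4 allows for dropout ("We anticipate no more than 20% dropout during the 4-week intervention"), "which would result in about 24 observations at each of the 4 doses". It then states one precision figure, for the optimal dose: "This sample size would allow us to estimate the effect size of the optimal dose within 0.37 units (80% CI), or 0.57 (95% CI"). Its only caveat is that the mixed model should do somewhat better than this least favourable case.

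Section 9.3.1 says that, where tests are done, "significance will be judged at 5% level, two-sided". Neither the protocol nor its statistical section mentions simultaneous intervals, shrinkage, sample splitting or any other allowance for picking the best dose.

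**The concern.** No dose is named as optimal beforehand. It will be whichever of three noisy contrasts comes out highest, and the highest of several noisy estimates tends to be one whose error was positive. Its raw value therefore overstates, on average, the true effect of the dose chosen. The half-widths in section 9.4 describe a different quantity: a single contrast fixed before the data are seen.

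Sections 9.1 and 9.3.1 put the weight on effect sizes and confidence intervals rather than on tests, so bias in the headline effect size bears on the main result. The same number is compared with 0.5, so the error makes a Go more likely.

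**Working it through.** **Inputs from the documents.** 30 participants (4.3); 20% dropout, so 30 × 0.8 = 24 per condition (9.4); three active doses and a shared sham (9.3.2); the dose with the largest effect is sought (3.1); Go threshold 0.5 (3.5.1).

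**Assumptions.** The documents give neither the within-subject correlation ρ nor the true effect at each dose, so both are varied. The effect size is taken as the mean difference over the SD of a single measurement, because that scaling reproduces the plan's figures. Errors are normal with equal correlation between sessions.

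**1. The plan's figure.** Half-width = z × sqrt(2/24), with sqrt(2/24) = 0.2887.
- 80%: 1.2816 × 0.2887 = 0.370
- 95%: 1.9600 × 0.2887 = 0.566

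Both match 0.37 and 0.57. This is the formula for two independent sets of 24 and one prespecified contrast, which corresponds to ρ = 0.

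**2. Bias of the selected dose when true effects are equal.** The sham error is common to the three contrasts and averages zero. The bias is therefore the expected maximum of three independent normal errors, 3/(2√π) = 0.846 standard errors of one dose mean (after the shared participant effect cancels):

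bias = 0.846 × sqrt((1 − ρ)/24)
- ρ = 0: 0.846 × 0.2041 = 0.173
- ρ = 0.5: 0.846 × 0.1443 = 0.122

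Against the threshold, 0.173/0.5 = 35% and 0.122/0.5 = 24%.

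**3. Other patterns of true effects.** From simulation, bias is the raw estimate minus the true effect of the dose selected.

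| True effects | Bias, ρ = 0 | Bias, ρ = 0.5 |
|---|---|---|
| all equal | 0.17 | 0.12 |
| 0.3 / 0.5 / 0.3 | 0.14 | 0.08 |
| 0 / 0.5 / 0 | 0.05 | 0.01 |
| 0 / 1.54 / 0 | 0.00 | 0.00 |

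**4. Chance of passing 0.5 when no dose works.**
- One prespecified dose, ρ = 0: 0.5/0.2887 = 1.73, upper tail 4.2%. Best of three, by simulation: 10.0% (9.7% if not all doses may pass).
- One prespecified dose, ρ = 0.5: SE = sqrt(2 × 0.5/24) = 0.204, 0.5/0.204 = 2.45, upper tail 0.7%. Best of three: about 2%.

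**5. Coverage.** Two intervals need to be kept apart.
- *The model's own interval for the selected dose*, equal effects: 76.6% (nominal 80%) and 93.6% (nominal 95%), at either correlation. The interval lies wholly above the truth in 21.8% of trials instead of 10%, and in 6.3% instead of 2.5%. At true effects 0/0.25/0.5 and ρ = 0, coverage is 79.3% and 94.6%.
- *The literal widths 0.37 and 0.57*, equal effects: 76.6% and 93.8% at ρ = 0; 80.5% and 95.7% at ρ = 0.15; about 91% and 99% at ρ = 0.5.

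**The case against.** The best defence is that this is an early-phase estimation study. Section 9.3.2 already yields all three contrasts, so a reader of the results can see that a choice was made. Section 9.4 presents its figures as the unfavourable case. The Go rule looks for an effect at one dose but not all, so it expects unequal doses, and the bias shrinks as one dose pulls ahead.

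Much of this stands, and it rules out three stronger readings.
- A reader might infer that the stated 80% and 95% levels fail badly. They do not. The worst loss is 80 − 76.6 = 3.4 points and 95 − 93.6 = 1.4 points. The literal widths under-cover only when the correlation is near zero, and the documents do not give that correlation.
- A reader might infer that Dunnett-type simultaneous intervals are required and that the promised precision must worsen. Their multipliers, 1.73 and 2.35, give half-widths of 0.50 and 0.68 at ρ = 0, but 0.35 and 0.48 at ρ = 0.5, which are narrower than those stated. They protect all three contrasts jointly. For the selected dose they are conservative (about 90% and 97.5% coverage at equal effects), and they leave the bias in place.
- A reader might infer that the inflated figure will be used to plan the next study. Section 9.1 says only that strategies may be tested in later confirmatory studies; the documented use is the Go/No-Go comparison.

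The defence does not answer the bias. The caveat in 9.4 concerns the gain from the mixed model, not selection. Showing three contrasts does not correct the one compared with 0.5, and the documents do not establish that one dose will dominate.

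**Conclusion.** The point holds as a missing allowance for selection. The arithmetic in section 9.4 is correct, but it is attached to a dose that will be chosen from the data. The material consequence is upward bias in the estimate compared with 0.5: about 0.17 SD (ρ = 0) or 0.12 (ρ = 0.5) if the three doses are equally effective, 0.14 or 0.08 for 0.3/0.5/0.3, and close to zero if one dose stands clearly apart. With no true effect at ρ = 0, choosing the best of three raises the chance of an observed d above 0.5 from about 4% to about 10%. Under-coverage is secondary, though its misses fall mostly on the high side.

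These sizes rest on 24 participants per condition, normal errors and assumed values for the correlation and the true effects. The direction of the bias does not depend on the values assumed.

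**What to change.** 1. In section 9.4, state that 0.37 and 0.57 apply to a single dose-sham contrast fixed in advance and do not account for choosing the best of three.
2. In section 9.3.2, commit to reporting all three dose-sham effect sizes with their intervals, whichever dose is selected.
3. Prespecify a bootstrap selection-corrected estimate for the selected dose: resample participants with all their sessions, repeat the model and the choice of dose in each resample, and subtract the average excess of the winning estimate over that dose's value in the original data. Show it beside the raw estimate wherever either is compared with 0.5, including in section 3.5.1. In simulation with equal effects, such a correction cut the bias from 0.17 to about 0.05 at ρ = 0 and from 0.12 to about 0.035 at ρ = 0.5.

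Dunnett-type intervals may be added if joint statements about all three doses are wanted; they do not replace step 3.

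The cost is a few sentences and slightly more analysis, with no change to design, sample size or data collection. The headline estimate becomes less favourable, and its root mean squared error rises slightly when one dose is moderately ahead. The text should be settled before results by dose are seen.

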3.4 Description of Study Design

We will compare the effect of three t-PBM doses (high, middle, and low irradiance) to sham t-PBM on PFC CBF as assessed with fMRI (BOLD) in this multi-center, phase I, single-blind, dose-ranging, crossover study of 30 subjects with MDD. All eligible participants will undergo four sessions of t-PBM during fMRI so that they experience irradiances of 50, 300 and ≥ 700 mW/cm 2 as well as sham. The order of dose administration will be randomized and t-PBM will be administered with the LightForce® EXPi Deep Tissue Laser Therapy™ System, Transcranial PhotoBioModulation-1000 (tPBM-2.0).

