9.3.2 Analysis of the Primary Efficacy Endpoint(s)

For each subject at each t-PBM dose (including sham) we will obtain the BOLD signal change measured in left and right dorsolateral prefrontal cortical regions of interest. These measures will be modeled as a function of dose (considered a categorical variable with 4 levels) using mixed effects models¹¹⁷, including random subject intercepts to account for the potentially correlated measures on the same subject. Since the doses will be presented to subjects in a random order, the initial model will also include order of the dose (a continuous variable) and all interactions between the dose and the order. If there is evidence for an interaction effect between dose and order, this effect will be investigated to understand how the dose effect varies as a function of week of treatment, and in such case effect size of the t-PBM doses will be estimated using only the data when the dose was given in the first week. If there is no interaction between dose and order, the order variable and the interactions will be omitted and the resulting model will be used to estimate the mean BOLD signal measures at each dose and the differences between each active t-PBM dose and sham.

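### The precision that Section 9.4 calls a worst case does not cover the first-week-only rule in Section 9.3.2, under which the interval is about 1.8 to 2 times as wide

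*Combined protocol and SAP*

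**What the plan says.** Section 9.4 starts from 30 treated participants (Section 4.3: "We intend to enroll 30 subjects over 24 months") and allows for dropout: "We anticipate no more than 20% dropout during the 4-week intervention", "which would result in about 24 observations at each of the 4 doses". From this it concludes that the trial can "estimate the effect size of the optimal dose within 0.37 units (80% CI), or 0.57 (95% CI". It gives no formula, no within-subject correlation and no definition of the SD behind the effect size. It adds that the analysis is a "mixed effects model which will provide somewhat better power than the one reported above under worst-case scenario".

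The design is a crossover (Section 3.4: "All eligible participants will undergo four sessions of t-PBM during fMRI so that they experience irradiances of 50, 300 and" the high dose, and sham as well). The primary model in Section 9.3.2 is a mixed model with random subject intercepts, fitted first with dose, order and their interaction. If there is evidence of an interaction, the "effect size of the t-PBM doses will be estimated using only the data when the dose was given in the first week". Section 9.4 does not mention the precision of that path.

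Section 3.5.1 sets the Go decision at a Cohen's d of 0.5 against sham. Section 9.1 puts the emphasis on estimation with effect sizes and confidence intervals, not on testing.

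**The concern.** Section 9.4 gives no power calculation, so the half-widths of 0.37 and 0.57 are the quantitative justification of the sample size. A reader who is told that these are worst-case figures will take 0.57 as the widest 95% half-width that the plan can produce.

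The plan contains a pre-specified path that produces a much wider one. The first-week rule turns the crossover into a four-arm parallel comparison with about a quarter of the participants in each arm. If that path is taken, the estimate that feeds the Go/No-Go decision carries far more uncertainty than Section 9.4 discloses.

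A second gap is the missing standardiser. Without it, one cannot tell whether the mixed model should do better than 0.37/0.57 at all.

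**Working it through.** **Inputs.** 30 participants and 20% dropout, so 30 x 0.8 = 24 per dose (Sections 4.3 and 9.4). Eight orders from two 4x4 Latin squares at each site (Section 9.5.1), so each of the four conditions comes first in 2 of 8 orders, a quarter. Two-sided normal quantiles: 1.2816 (80%) and 1.96 (95%). The within-subject correlation rho is not in the documents; a range is shown as an assumption.

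**1. The stated figures.** For a standardised difference between two independent means with 24 observations each, the half-width is z*sqrt(1/24 + 1/24) = z*sqrt(2/24).

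- 80%: 1.2816 x 0.2887 = 0.370
- 95%: 1.96 x 0.2887 = 0.566

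These match 0.37 and 0.57. Other natural candidates do not: paired, scaled by the SD of the differences, gives 0.26/0.40; n = 30 gives 0.33/0.51; one-sided limits give 0.24/0.47.

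**2. Full-data crossover, d scaled by the total SD.** The half-width is z*sqrt(2(1 - rho)/24).

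| rho (assumed) | 80% | 95% |
|---|---|---|
| 0 | 0.37 | 0.57 |
| 0.3 | 0.31 | 0.47 |
| 0.5 | 0.26 | 0.40 |
| 0.7 | 0.20 | 0.31 |

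A random-intercept model implies rho of at least 0, so 0.37/0.57 is the upper bound over correlation on this scale.

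**3. Full-data crossover, d scaled by the within-subject residual SD.** The variance of the dose-sham difference is 2(1 - rho)/24 of the total variance, and the residual variance is (1 - rho) of it. The correlation cancels and z*sqrt(2/24) applies at any rho. A simulation with 24 participants (20,000 runs at each rho of 0, 0.3, 0.5 and 0.7) gave a 95% half-width of 0.57 to 0.58 throughout. On this scale 0.57 is about what the mixed model delivers, and there is no gain still to come.

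**4. First-week rule.** Each comparison is between different people, so the half-width on the total-SD scale is z*sqrt(2/n), with n participants per condition in week one.

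| n per dose | 80% | 95% | ratio to stated |
|---|---|---|---|
| 30/4 = 7.5 | 1.2816 x 0.5164 = 0.66 | 1.96 x 0.5164 = 1.01 | sqrt(24/7.5) = 1.79 |
| 24/4 = 6 | 1.2816 x 0.5774 = 0.74 | 1.96 x 0.5774 = 1.13 | sqrt(24/6) = 2.00 |

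With t quantiles the 95% half-width is about 1.06 (7.5 per dose, variance pooled over four groups) to 1.29 (6 per dose, two groups). If d were scaled by the residual SD, these half-widths would be divided by sqrt(1 - rho) and so would be wider still for any positive rho.

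**5. Against the Go threshold.** An observed d of 0.5 has a 95% interval of 0.5 +/- 0.57 = -0.07 to 1.07 at the stated half-width. Under the first-week rule it is 0.5 +/- 1.01 = -0.51 to 1.51, or 0.5 +/- 1.13 = -0.63 to 1.63. The 95% half-width is 1.01/0.5 = 2.0 to 1.13/0.5 = 2.3 times the threshold.

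**The case against.** The strongest defence is that Section 9.4 describes the planned full-data analysis, and that worst case there means ignoring correlation. In that sense, on the total-SD scale, the label is right, and the paragraph discloses the simplification when it says that the model "will provide somewhat better power than the one reported above under worst-case scenario". This stands. A reader who recognises the independent-groups formula might infer that the figures are an arithmetic error or use a formula that is wrong for a crossover. The documents do not support that: the figures are a conservative bound on one scale and the crossover result itself on the other.

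A reader might also infer that the trial is substantially more precise than stated. That needs both the total SD as standardiser and a sizeable rho. The documents give neither. The endpoint is a BOLD signal change, which already removes much of the stable difference between people, so a low correlation between sessions is a reasonable planning assumption.

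Nor does the point show that a Go decision would come out differently. Section 3.5.1 sets the rule on the size of d and does not require the interval to exclude zero.

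On the first-week rule, the defence is that it is conditional and belongs to Section 9.3.2, and that 6 per dose is pessimistic because Section 9.4 places dropout during the four weeks. The second part stands: 7.5 per dose, and a ratio of about 1.8, is the more likely case. The first part does not remove the problem. The rule is pre-specified for the primary endpoint, and a figure labelled worst case invites the reader to apply it to every path in the plan.

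**Conclusion.** The point holds in this form: 0.37/0.57 is a valid zero-correlation bound for the full-data analysis on the total-SD scale, but it is not the worst case of the plan as written. Under the first-week rule the 80%/95% half-widths are about 0.66/1.01 with 7.5 per dose and 0.74/1.13 with 6, which is 1.8 to 2 times the stated values, with the 95% half-width at least twice the Go threshold. Separately, because the standardiser is not named, the promise of better precision cannot be checked, and it fails if d uses the residual SD.

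The first-week figures assume even allocation over the eight orders, first-week data for sham as well as for the active doses, the total SD as standardiser and normal quantiles. They do not depend on rho. How likely the interaction rule is to be triggered cannot be judged from the documents.

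The point does not show that the sample size is too small for the full-data analysis.

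**What to change.** Revise the one paragraph in Section 9.4:

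- Name the SD that standardises Cohen's d, and use the same definition for the Go threshold in Section 3.5.1.
- Present 0.37/0.57 as the zero-correlation bound for the full-data analysis only. Half-widths over an assumed correlation range, for example 0 to 0.7, may be added. If the residual SD is chosen, withdraw the statement that the mixed model will do better.
- Either delete the worst-case label, or report the first-week-only half-width (about 0.66/1.01 with 7.5 per dose, 0.74/1.13 with 6) as the worst case.

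The cost is a rewording. The stated worst-case precision becomes less favourable; sample size, randomisation and conduct do not change.

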9.5.2 Evaluation of Success of Blinding

We will use the placebo blinding questionnaire (PBQ) to evaluate the success of blinding.

10 Source Documents and Access to Source Data/Documents

Source data is all information, original records of clinical findings, observations, or other activities in a clinical trial necessary for the reconstruction and evaluation of the trial. Source data are contained in source documents. Examples of these original documents, and data records include: hospital records, clinical and office charts, laboratory notes, memoranda, subjects' diaries or evaluation checklists, pharmacy dispensing records, recorded data from automated instruments, copies or transcriptions certified after verification as being accurate and complete, microfiches, photographic negatives, microfilm or magnetic media, x-rays, subject files, and records kept at the pharmacy, at the laboratories, and at medico-technical departments involved in the clinical trial. It is acceptable to use CRFs as source documents. If this is the case, it should be stated in this section what data will be collected on CRFs and what data will be collected from other sources.

The study case report form (CRF) is the primary data collection instrument for the study. All data requested on the CRF must be recorded. All missing data must be explained. If a space on the CRF is left blank because the procedure was not done or the question was not asked, write "N/D". If the item is not applicable to the individual case, write "N/A". All entries should be printed legibly in black ink. If any entry error has been made, to correct such an error, draw a single straight line through the incorrect entry and enter the correct data above it. All such changes must be initialed and dated. DO NOT ERASE OR WHITE OUT ERRORS. For clarification of illegible or uncertain entries, print the clarification above the item, then initial and date it.

Access to study records will be limited to IRB-approved members of the study team. The investigator will permit study-related monitoring, audits, and inspections by the IRB/EC, the sponsor, government regulatory bodies, and University compliance and quality assurance groups of all study related documents (e.g. source documents, regulatory documents, data collection instruments, study data etc.).

The investigator will ensure the capability for inspections of applicable study-related facilities (e.g. pharmacy, diagnostic laboratory, etc.).

Participation as an investigator in this study implies acceptance of potential inspection by government regulatory authorities and applicable University compliance and quality assurance offices.

11 Quality Assurance and Quality Control

QC procedures will be implemented beginning with the data entry system and data QC checks that will be run on the database will be generated. Any missing data or data anomalies will be communicated to the site(s) for clarification/resolution.

Following written SOPs, the data coordinating center will verify that the clinical trial is conducted and data are generated, documented (recorded), and reported in compliance with the protocol, GCP, and the applicable regulatory requirements.

The investigational site will provide direct access to all trial related sites, source data/documents, and reports for the purpose of monitoring and auditing by the sponsor, and inspection by local and regulatory authorities.

12 Ethics/Protection of Human Subjects

